6.9 Unacceptable toxicity requiring treatment discontinuation

If one study drug is discontinued for unacceptable toxicity, treatment with the other agent will also be discontinued.

6.9.1 Unacceptable toxicity from sorafenib

The decision to discontinue sorafenib for toxicity should follow local standards of care as guided by the FDA label for sorafenib in HCC. Grade ≥ 4 AE attributed to sorafenib require discontinuation of sorafenib.

6.9.2 Unacceptable toxicity related to nivolumab

Treatment with nivolumab should be permanently discontinued for the following toxicities attributed to nivolumab therapy:

- 1. Any Grade ≥ 2 ophthalmologic irAE such as uveitis causing eye pain or reduction of visual acuity that does not improve to Grade ≤ 1 severity within 14 days of starting topical therapy or requires systemic treatment
- 2. Any Grade ≥ 3 non-skin, drug-related adverse event that does not downgrade to Grade ≤ 2 within 7 days with optimal medical management including systemic corticosteroids and/or hormone replacement and/or does not downgrade to ≤ Grade 1 or baseline within 14 days, with the following exceptions:
 - a. Any Grade ≥ 2 pneumonitis irAE that does not improve to ≤ Grade 1 within 7 days of initiation of maximal supportive care requires discontinuation
 - Any event of Grade ≥ 3 drug-related uveitis, bronchospasm, pneumonia or pneumonitis, hypersensitivity reaction, or infusion reaction regardless of duration requires discontinuation
 - c. Grade 3 drug-related endocrinopathies adequately controlled with only physiologic hormone replacement do not require discontinuation
 - d. Asymptomatic/uncomplicated Grade 3 drug-related laboratory abnormalities do not require treatment discontinuation
- 3. Hepatotoxicity as evidenced by the following lab values requires discontinuation:

- a. AST or ALT > 8 x ULN for > 2 weeks, irrespective of baseline
- b. AST or ALT > 15 x ULN irrespective of baseline or duration
- c. Total bilirubin > 5 x ULN, irrespective of baseline or duration
- 4. Any Grade 4 drug-related adverse event or laboratory abnormality requires discontinuation, except for the following events which do not require discontinuation:
 - a. Grade 4 neutropenia < 7 days
 - b. Grade 4 lymphopenia or leukopenia
 - Isolated Grade 4 amylase or lipase abnormalities that are not associated with symptoms or clinical manifestations of pancreatitis including no evidence of pancreatitis on CT or MRI imaging
 - d. Isolated Grade 4 electrolyte imbalances or abnormalities that are not associated with clinical sequelae and are corrected with supplementation and appropriate management within 7 days of their onset
 - e. Grade 4 drug-related endocrinopathies adequately controlled with only physiologic hormone replacement do not require discontinuation
- 5. Any dosing delay for treatment-related toxicity lasting > 6 weeks (42 days) with the following exceptions:
 - a. Dosing delays up to 12 weeks to allow for prolonged steroid tapers to manage drug-related irAE are allowed with approval from Study Chair.

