6.7.2 Nivolumab dose modifications and delays

No dose reductions for nivolumab are permitted under this protocol. Nivolumab administration will be delayed for the following:

- 1. Any Grade ≥ 2 non-skin drug-related adverse event, with the following exceptions:
 - a. Grade 2 drug-related fatigue or asymptomatic laboratory abnormalities do not require a treatment delay.
- 2. Any Grade ≥ 3 skin drug-related adverse event.
- 3. Any Grade ≥ 3 drug-related laboratory abnormality with the following exceptions:
 - Grade 3 amylase or lipase abnormalities that are not associated with symptoms or clinical manifestations of pancreatitis do not require a dose delay.
- 4. Dose delay for changes in AST or ALT as follows:
 - a. If a subject has a baseline AST or ALT that is within normal limits, delay dosing for drug-related Grade > 2 toxicity (2 grade shift).
 - b. If a subject has baseline AST or ALT within the Grade 1 toxicity range, delay dosing for drug-related increase to ≥ 8x ULN.
 - c. If a subject has baseline AST or ALT within the Grade 2-3 toxicity range, delay dosing for two-fold drug-related increase in AST or ALT or for AST or ALT values 10x ULN (whichever is lower).
- 5. Any adverse event, laboratory abnormality, or intercurrent illness which, in the judgment of the investigator, warrants delaying the dose of study medication.

See Section 6.8.2 and Appendix 14.5 for guidance on management of toxicity attributed to nivolumab including initiation of immunosuppression for possible immune-related toxicity. Subjects who require delay of nivolumab should be re-evaluated weekly or more frequently if clinically indicated. It is recommended to monitor elevations in AST or ALT at least weekly until levels peak or begin to decline. Nivolumab dosing can be resumed when the following re-treatment criteria are met.

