6.7.2.1 Criteria to resume nivolumab dosing after delay for toxicity

Subjects may resume treatment with a study drug after treatment hold for toxicity if the drug-related AE(s) resolve to Grade ≤ 1 or baseline within 6 weeks (42 days), with the following exceptions:

- 1. Subjects may resume treatment in the presence of Grade 2 fatigue.
- 2. Subjects who have not experienced a Grade 3 drug-related skin AE may resume treatment in the presence of Grade 2 skin toxicity.
- 3. Subjects with baseline Grade 1 AST, ALT, or total bilirubin who require dose delays for reasons other than a drug-related hepatic event may resume treatment in the presence of Grade 2 AST, ALT, or total bilirubin.
- 4. Subjects who require dose delays for drug-related elevations in AST, ALT, or total bilirubin may resume treatment when these values have returned to their baseline CTCAE Grade or normal, provided the criteria for unacceptable toxicity requiring permanent discontinuation are not met (Section 6.9).
- 5. Drug-related pulmonary toxicity, diarrhea, or colitis must have resolved to baseline before treatment is resumed.
- 6. Drug-related endocrinopathies adequately controlled with only physiologic hormone replacement are acceptable for resuming treatment.
- 7. A longer treatment delay up to approximately 12 weeks for recovery of treatment-related toxicity in subjects may be permitted in subjects who have demonstrated previous treatment benefit (e.g. radiographic regression and/or clinical improvement such as reduced pain or tumor marker), with approval from Study Chair or designee.

If the criteria to resume treatment are met, the subject should restart treatment at the next scheduled time point per protocol.

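### For some nivolumab-attributed Grade 3 non-skin events, Section 6.7.2.1 permits restart while Section 6.9.2 item 2 requires a permanent stop, and neither section says in general which governs

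*Combined protocol and SAP*

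**What the plan says.** **Permanent stop.** Section 6.9.2 item 2 applies to Grade 3 or higher non-skin events attributed to nivolumab. It has two limbs joined by 'and/or': no fall to Grade 2 or lower within 7 days, and an event that "does not downgrade to ≤ Grade 1 or baseline within 14 days, with the following exceptions". The listed exceptions deal with pneumonitis, a group of events that stop treatment at any duration, controlled Grade 3 endocrinopathies, and asymptomatic Grade 3 laboratory values. Fatigue is not listed. Item 5 of the same section separately stops treatment for a toxicity delay of more than 42 days.

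**Restart.** Section 6.7.2.1 lets a held subject resume if the drug-related events "resolve to Grade ≤ 1 or baseline within 6 weeks (42 days), with the following exceptions". The first exception is "Subjects may resume treatment in the presence of Grade 2 fatigue". Neither provision is limited by the grade at which the event began. The section closes by saying that a subject who meets the criteria should restart at the next scheduled time point. Only item 4, on AST, ALT and bilirubin, is made subject to the stopping rules: "provided the criteria for unacceptable toxicity requiring permanent discontinuation are not met (Section 6.9".

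**Hold.** Section 6.7.2 item 1 delays nivolumab for "Any Grade ≥ 2 non-skin drug-related adverse event", but "Grade 2 drug-related fatigue or asymptomatic laboratory abnormalities do not require a treatment delay".

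**Effect on sorafenib.** Section 6.9 states: "If one study drug is discontinued for unacceptable toxicity, treatment with the other agent will also be discontinued".

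**The concern.** Both sections can apply to the same patient on the same day, one permitting restart and the other requiring a permanent stop. Because a required hold for fatigue itself begins at Grade 3, the Grade 2 fatigue exception most directly meets patients who also fall under 6.9.2 item 2. Such a patient could restart before day 14 and then have to stop for good on day 14 at an unchanged grade. For other non-exempt events, the 42-day restart window stays open after the 14-day stop has taken effect.

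At stake is whether the patient keeps or loses both drugs. That affects patient handling, treatment exposure, and the discontinuations for toxicity summarised under Section 8.2.2.1. In a 12-patient cohort at two sites, even one patient handled differently would show in that summary.

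**Working it through.** The plan gives no figure to reproduce, so the check sets the rules side by side by starting grade, grade reached and day. Days are counted from onset, and the hold is taken to begin at onset; the sections do not state a common origin, so this is an assumption. All cases concern a Grade 3 non-skin event attributed to nivolumab, with baseline below Grade 2.

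**Step 1: remove events where there is no conflict.** Controlled endocrinopathies and asymptomatic laboratory values are exempt from item 2. Uveitis, bronchospasm, pneumonia or pneumonitis, hypersensitivity and infusion reactions of Grade 3 or higher stop at any duration. Restart after AST, ALT or bilirubin holds is expressly subject to Section 6.9.

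**Step 2: apply both rules to what is left.**

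| Course of the event | 6.7.2.1 | 6.9.2 item 2, 'or' | 6.9.2 item 2, 'and' |
|---|---|---|---|
| (i) Fatigue, Grade 2 by day 7, still Grade 2 on day 14 | Restart permitted (item 1) | Permanent stop at day 14 | No stop: first limb not met |
| (ii-a) Other event, Grade 2 by day 7, first at Grade ≤1 or baseline on days 15–42 | Restart permitted | Permanent stop at day 14 | No stop: first limb not met |
| (ii-b) Event still Grade 3 after day 7, first at Grade ≤1 or baseline on days 15–42 | Restart permitted | Permanent stop after day 7 | Permanent stop at day 14 |

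Under 'or', all three rows conflict. Under 'and', rows (i) and (ii-a) are consistent and row (ii-b) still conflicts. Fatigue still Grade 3 after day 7 that is at Grade 2 on or after day 14 behaves like row (ii-b), because item 1 of 6.7.2.1 permits restart at that grade. No reading of 'and/or' alone removes the conflict.

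**Step 3: length of the overlap.** Days 15 to 42 are 42 − 14 = 28 days. For subjects with previous benefit and Study Chair approval, 6.7.2.1 item 7 extends the delay to about 12 weeks (12 × 7 = 84 days), so the overlap can run to about day 84.

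**Step 4: is precedence stated?** Restart is made subject to the stopping criteria after a DLT (Section 6.2.3), for liver tests (6.7.2.1 item 4) and for hepatic events (Appendix 6). No such statement covers restart in general.

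**Step 5: effect on the Part 2 primary endpoint.** Section 8.2.1.2 defines it as the rate of Grade 3 or higher related events and attaches confidence intervals for a proportion of 12 patients. Item 2 is reached only after such an event, so an affected patient is already counted whichever rule is followed.

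**The case against.** The strongest reply is that 6.9.2 simply prevails. Section 6.10 item 1 discontinues treatment for unacceptable toxicity under Section 6.9, while 6.7.2.1 opens permissively. Section 6.9.2 lists the 14-day and 42-day limits as separate stops, so 42 days can be read as a residual cap. The longer window would still serve Grade 2 non-skin events, Grade 3 skin events and the exempt categories, so it would not be redundant. This reading is coherent, and it may be what was intended. But it is not stated. The restart section ends by saying that the subject should restart, the stop section also uses 'should', and attaching the proviso to the liver-test item alone invites the inference that the other items are free of it. The general principles in Section 6.7 also give 42 days with no shorter limit for Grade 3.

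A second reply is that the fatigue exception has other uses. A reader might infer that Grade 2 fatigue can never lead to a hold. The documents say only that a delay is not required, and Sections 6.7 and 6.7.2 item 5 leave the investigator free to hold. The exception can also cover a patient held for another event who has fatigue as well. This stands: fatigue that was Grade 3 is one use of the exception, and the conflict is confined to it.

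Third, the weekly Site Committee review in Appendix 11 covers events from both sites. That reduces the risk of divergent handling, but the review as described concerns toxicity, grade and attribution, not which of the two sections decides restart.

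**Conclusion.** The conflict is real but bounded. It concerns nivolumab-attributed Grade 3 non-skin events outside the item 2 exceptions, the any-duration stops and the liver-test proviso. Case (i) depends on reading 'and/or' as 'or'. Case (ii) holds in full under 'or', and under 'and' only for events still Grade 3 after day 7. It affects whether both drugs continue, exposure, and the 8.2.2.1 discontinuation summary. It merits correction but does not threaten the primary analysis.

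Three stronger inferences are not supported:

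- **All Grade 3 non-skin events are affected.** They are not; several categories are exempt, stop regardless of duration, or are already subject to Section 6.9.
- **The Part 2 primary endpoint is distorted.** The affected patient's status is fixed by the event that triggers the rule.
- **The frequency can be calculated.** A reader might take the Grade 3–4 fatigue rates of 3.4% (sorafenib, Asian phase III, Section 1.3.2) and 15% (nivolumab plus pazopanib, Section 1.5.2), giving 12 × 0.034 = 0.4 to 12 × 0.15 = 1.8 patients. Or they might take the 24.5–36% related Grade 3 or higher rates in Section 8.2.1.2, giving 12 × 0.245 = 2.9 to 12 × 0.36 = 4.3. None of these counts the relevant events. The 3.4% is from sorafenib alone, the 15% from another combination in renal cell carcinoma, and the 36% from a sorafenib registry. The overall related-event rates are not restricted to non-skin, non-exempt Grade 3 events. None of the figures separates events that had recovered by day 14. The share recovering between days 15 and 42 is not given, so the number affected cannot be estimated.

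**What to change.** Reconcile Section 6.7.2.1 with Section 6.9.2 item 2, and make four changes:

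- Say whether 'and/or' in item 2 means that either limb or both limbs must fail.
- State which section governs Grade 3 fatigue that falls to Grade 2 and remains there on day 14.
- State which section governs other non-exempt Grade 3 events that first reach Grade 1 or baseline between days 15 and 42.
- Put the same precedence statement in both sections, and summarise toxicity discontinuations under 8.2.2.1 according to the reconciled rule.

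Which limit applies is a clinical decision for the sponsor. The cost is amendment wording in two sections, with no added visits, tests or patients.

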APPENDIX 6: irAE management

The following algorithms from Nivolumab IB (v.15.0) represent clinical guidance to the treating investigator for management of selected irAE which have been associated with nivolumab. Additional management including optimal supportive care should be employed in all cases as clinically appropriate, according to clinical judgment of treating investigator. Subspecialty consultation for additional management recommendations should be obtained whenever needed, e.g. for severe or refractory cases, at discretion of treating investigator.

Endocrine irAE*

Endocrinopathy Management Algorithm

Rule out non-inflammatory causes. If non-inflammatory cause, treat accordingly and continue I-O therapy. Consider visual field testing, endocrinology consultation, and imaging.

[figure not shown]
Patients on IV steroids may be switched to an equivalent dose of oral corticosteroids (e.g. prednisone) at start of tapering or earlier, once sustained clinical improvement is observed. Lower bioavailability of oral corticosteroids should be taken into account when switching to the equivalent dose of oral corticosteroids.

*For cases with new onset diabetes mellitus, the role for steroid therapy is unknown and consultation with Endocrinologist is strongly recommended. For symptomatic diabetes, nivolumab should be withheld, and insulin replacement should be initiated as needed. Monitoring of blood sugar should continue to ensure appropriate insulin replacement is utilised. Nivolumab must be permanently discontinued for life-threatening diabetes.

GI irAE

GI Adverse Event Management Algorithm

Rule out non-inflammatory causes. If non-inflammatory cause is identified, treat accordingly and continue I-O therapy. Opiates/narcotics may mask symptoms of perforation. Infliximab should not be used in cases of perforation or sepsis.

Patients on IV steroids may be switched to an equivalent dose of oral corticosteroids (e.g. prednisone) at start of tapering or earlier, once sustained clinical improvement is observed. Lower bioavailability of oral corticosteroids should be taken into account when switching to the equivalent dose of oral corticosteroids.

Hepatic irAE

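### Stopping rule (6.9.2 item 4e) and restart rule (6.7.2.1 item 6) for controlled endocrinopathies conflict with the Appendix 6 stop for life-threatening diabetes, and no text says which prevails (low severity)

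*Combined protocol and SAP*

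**What the plan says.** Section 6.9.2 lists the toxicities that end nivolumab permanently. Item 4 covers Grade 4 drug-related events and laboratory abnormalities, with five exceptions. The last, item 4e, states: "Grade 4 drug-related endocrinopathies adequately controlled with only physiologic hormone replacement do not require discontinuation".

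Section 6.7.2.1 lists the conditions for resuming nivolumab after a delay. Item 6 states: "Drug-related endocrinopathies adequately controlled with only physiologic hormone replacement are acceptable for resuming treatment". It has no grade limit and no exception for diabetes.

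Item 2 of 6.9.2 is a separate stop based on time to recovery. It applies to "Any Grade ≥ 3 non-skin, drug-related adverse event that does not downgrade to Grade ≤ 2 within 7 days with optimal medical management", and also to an event that has not reached Grade 1 or baseline within 14 days. Its endocrine exception, item 2c, is limited to Grade 3: "Grade 3 drug-related endocrinopathies adequately controlled with only physiologic hormone replacement do not require discontinuation".

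Appendix 6 deals with new-onset diabetes in a note to the endocrine algorithm. For symptomatic diabetes it withholds nivolumab and says that "insulin replacement should be initiated as needed". It ends: "Nivolumab must be permanently discontinued for life-threatening diabetes". The appendix opens by saying that its algorithms "represent clinical guidance to the treating investigator for management of selected irAE which have been associated with nivolumab".

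Section 6.9 adds that stopping either drug for unacceptable toxicity also stops the other.

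**The concern.** Consider a patient with Grade 4 immune-related diabetes that is brought under control quickly on insulin. A site working from the stopping and restarting sections can conclude that nivolumab need not be stopped and may be resumed. A site working from Appendix 6 must stop it permanently. The protocol gives no order of precedence, and its own signals point both ways: the appendix calls itself guidance, yet its diabetes sentence is worded as an obligation.

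At stake is whether one patient is re-exposed after a life-threatening event and, through 6.9, whether that patient also stays on sorafenib. The choice also enters the summary of discontinuations for toxicity in 8.2.2.1.

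**Working it through.** **Step 1: the texts side by side.** The protocol gives no figure to reproduce on this point, so the first check is textual.

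| Text | Grade 4 diabetes, later controlled on insulin |
|---|---|
| 6.9.2 item 4e | stop not required |
| 6.7.2.1 item 6 | may resume |
| 6.9.2 item 2 | stop, if either recovery limit is missed |
| Appendix 6, endocrine note | stop permanently, if life-threatening |

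**Step 2: the links that bring one patient under all four.**
- Diabetes is an endocrinopathy. Appendix 6 places it under endocrine immune-related events.
- Insulin is physiologic hormone replacement. This is an assumption. Appendix 6 speaks of insulin as replacement but does not use the fuller term.
- Grade 4 diabetes is life-threatening. This is an assumption. The protocol describes Grade 4 in such terms for infusion reactions (6.8.2.2) and hemoglobin (Table 6.7.1-1), but it does not reproduce the CTCAE entry for diabetes.

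**Step 3: what item 2 removes.** Exception 2c covers Grade 3 only. A Grade 4 endocrine event is therefore stopped by item 2 unless it falls to Grade 2 or lower within 7 days and to Grade 1 or baseline within 14 days. Only events that meet both limits reach the conflict. Whether a patient who still needs insulin can be graded that low depends on CTCAE text that the protocol does not print, so the share may be zero. If 4e were instead read as overriding item 2, the share would be 100%.

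**Step 4: size.** Let p be the rate of Grade 4 immune-related diabetes and f the share of those events not stopped by item 2. The documents give neither, so both are assumed. Part 2 has n = 12 (8.4.2).

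P(at least one affected patient) = 1 − (1 − p·f)^12

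| p | f = 0 | f = 0.25 | f = 0.5 | f = 1 |
|---|---|---|---|---|
| 0.1% | 0% | 0.3% | 0.6% | 1.2% |
| 0.5% | 0% | 1.5% | 3.0% | 5.8% |
| 1% | 0% | 3.0% | 5.8% | 11.4% |

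For the largest cell: 1 − 0.99^12 = 0.114.

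**Step 5: effect on the results.** One such patient moves the Part 2 count of discontinuations for toxicity by 1/12 = 8.3 percentage points, provided the patient does not stop for another toxicity anyway. The number of patients with a grade 3 or higher treatment-related event, on which the Part 2 primary endpoint (8.2.1.2) rests, changes by 0, because the diabetes event is already counted.

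**The case against.** The strongest reply is that the texts can be reconciled. Item 4e is general and permissive, while the Appendix 6 sentence is specific and mandatory. Lifting a general stop for endocrinopathies does not forbid a specific stop for one of them. A site that stops complies with every text, and one that re-doses breaches a printed obligation. Section 6.7 lets the investigator stop for any toxicity. A life-threatening event is also an SAE, and SAEs are reviewed by the DSMC.

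This is a sensible reading and it leads to the same outcome as the fix. But the protocol does not state it. A site that takes Appendix 6 at its own description, as guidance, could let 6.9.2 govern and re-dose. The safeguards allow a stop but do not require one.

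Three further points for the other side stand:
- Item 2 may already stop every such case, which is why the range above starts at 0%.
- Item 4 of the restart list, on liver tests, allows resumption "provided the criteria for unacceptable toxicity requiring permanent discontinuation are not met (Section 6.9"), and item 6 has no such proviso. A reader might infer that item 6 can restart a drug that 6.9.2 has permanently stopped. It cannot: 6.9.2 and 6.10 item 1 end treatment on their own terms. The missing proviso adds little.
- Section 6.7.2 cites Appendix 14.5, which 7.2.5 identifies as BCLC staging, for toxicity management. A reader might infer that the diabetes rule cannot be reached from the main text. It can: the same sentence cites 6.8.2, and 6.8.2.1 names Appendix 14.6. That slip is clerical and forms no part of this point.

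The endocrine algorithm itself is a figure that is not available here, so the point rests on its printed note.

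**Conclusion.** The wording is inconsistent and should be corrected, at low severity. Items 4e and 6 permit continuing or resuming nivolumab after controlled Grade 4 endocrinopathy, Appendix 6 forbids it for life-threatening diabetes, and nothing ranks them. This holds if insulin is physiologic hormone replacement and Grade 4 diabetes is life-threatening, and only for events that 6.9.2 item 2 does not stop.

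Under the assumed rates, the chance of at least one affected patient among 12 is 0% to about 11%. This is an upper bound on harm, because harm also requires an investigator to choose to re-dose.

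A reader might infer that the protocol directs re-treatment after life-threatening diabetes. It does not: both items are permissive. Nor do the documents support any effect on the primary endpoint or on sample size. This is a matter of patient safety and consistent wording.

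**What to change.** Add to 6.9.2 item 4e and to 6.7.2.1 item 6 the clause: *except life-threatening diabetes, which requires permanent discontinuation (Appendix 6)*.

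The cost is one clause in each of two items, with no extra procedures, patients or data. It takes away no option that Appendix 6 leaves open. The appendix number in 6.7.2 can be corrected from 14.5 to 14.6 in the same amendment as a separate clerical change.
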